#### Sample size

Based on a major complication rate of 37.6%, reported in a prior study [11], 778 patients (389 per group) were required to have an 80% chance of detecting, as significant at the 5% level, a decrease in

the incidence of major complications from 37.6% in the control group (traditional technique) to 28.2% in the experimental group (positive pressure technique) (relative difference of 25%).

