### Statistical analysis

The primary analysis of outcomes was a per-protocol analysis. An intention-to-treat analysis was also performed. Thus, a “worst case scenario” method was adopted, assigning the event of interest to the patients lost to follow-up who were randomly assigned to the positive pressure group and not allocating the event of interest to the patients lost to follow-up who were randomly assigned to the traditional group. No interim analyses were planned. Chi-square test or Fisher exact test were used for the comparison categorical variables. Continuous variables with normal distribution were presented as mean and standard deviation (SD) and were compared with the Student's t test for independent samples. Non-normally distributed variables were presented as median with 25% and 75% percentiles. For outcome measures (primary and secondary), relative risks (RR) and 95% confidence intervals (CI) were calculated. Effect estimates were also reported with their absolute risk differences (ARD) and their corresponding 95% confidence intervals (95% CI). Tests were two-tailed, and a p-value  $<0.05$  was considered significant. Statistical analysis was performed using SPSS version 25.0; SPSS Inc, Chicago, IL, USA.

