### References

### Supplementary Material

Spontaneous breathing trial

Patients who met the eligibility criteria and successfully completed the spontaneous breathing trial (SBT) were immediately randomized. It was conducted with a T-tube, by applying continuous positive airway pressure (continuous positive pressure in the airway) at 5 cm H2O, or by applying pressure support (PS) from 5 to 8 cm H2O for a period ranging from 30 to 120 minutes. The oxygen flow rate or FiO2 was regulated to keep an oxygen saturation over 90%. After extubation, supplementary oxygen was administered with the same FiO2 used at the end of the successful SBT. All variables were collected and recorded in specific forms.

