### Procedure

Patients were included in the study once they had successfully completed the SBT and met the OTE criteria. The blinded evaluator followed a preextubation checklist. It entailed discontinuing enteral nutrition, adjusting the head of the bed to 45°, suctioning oropharyngeal and tracheobronchial

secretions, and recording preextubation monitoring on the pertaining sheet. Regardless of the procedure, the alarms were silenced, and the ventilator parameters were set at PS 15/10 cmH2O by one operator, so that the blinded evaluator could not hear the maneuver or read the ventilator parameters. The blinded evaluator left and was replaced by the operators, who knew about the technique assigned. They initiated the randomization through <http://extubar.ajrpt.com> and were in charge of the OTE and postextubation oxygen delivery. Regardless of the OTE technique, the patients received supplemental oxygen through a nasal cannula placed before ETT removal to keep the oxygen flow used in the SBT.

Once the OTE was completed, the blinded evaluator assessed the outcome measures recorded within 60 min after extubation. Daily monitoring of outcome measures within 72 h after extubation was carried out.

The decision to perform OTE and to use NIMV or HFNC to prevent OTE failure, follow-up, and treatment was taken by the blinded evaluator, or the respiratory therapist on duty, who was blinded to randomization assignment. If preventive NIMV or HFNC had previously been decided, it was implemented 15 min after OTE so as not to affect monitoring of outcome measures.

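### The primary comparison is unadjusted although baseline values are already collected, so it may give up some precision; the crude test itself is valid

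*Combined protocol and SAP*

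**What the plan says.** Methods, Statistical analysis: "Chi-square test or Fisher exact test were used for the comparison categorical variables". RR and ARD with 95% confidence intervals accompany the tests. No covariate, regression model or stratified test is mentioned. The primary analysis is per-protocol, with an intention-to-treat analysis alongside.

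Methods, Sample size: 778 patients (389 per group) "were required to have an 80% chance of detecting", "as significant at the 5% level", a fall in major complications from 37.6% to 28.2%. No allowance for exclusions is stated.

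Patient-level baseline information appears in three places:

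- Supplementary Material, Randomization: the high-risk stratum is defined by criteria that include age ≥ 66 and APACHE II ≥ 13 on the day before extubation.
- Supplementary Material, Procedure: the blinded evaluator's checklist includes "recording preextubation monitoring on the pertaining sheet". The evaluator then leaves, and the operators start the randomization.
- Supplementary Material, Spontaneous breathing trial: oxygen is regulated during the trial, and "All variables were collected and recorded in specific forms".

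None of these values, and neither stratification factor (center, high/low risk), enters the analysis.

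**The concern.** Desaturation within 15 minutes is one of the three components of the primary outcome. Preextubation oxygenation, age and severity of illness are natural candidates to predict it. The high/low flag retains little of that information: any one of a long list of criteria makes a patient high risk, and no oxygenation measurement is listed by name.

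Where baseline values are prognostic, a prespecified adjusted analysis gives a narrower interval for the same marginal RR and ARD, and more power, from the same patients. It also reduces the effect of chance imbalance in the values that are included.

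This matters because the design has no slack. Power is just under 80% with every patient analysed, and a per-protocol primary analysis can only lose patients.

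**Working it through.** **Inputs from the plan.** p₁ = 0.376, p₂ = 0.282, difference 0.094, two-sided 5%, 80% power, 389 per group.

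**Reproducing the plan's sample size.** Unpooled normal approximation:

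n = (1.960 + 0.842)² × [0.376 × 0.624 + 0.282 × 0.718] / 0.094² = 7.849 × 0.4371 / 0.008836 = 388.3, so 389 per group and 778 in total. This matches exactly. The pooled-variance form gives 392 per group.

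**Power of the planned crude test.** The mean rate is 0.329.

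- Null SE = √(2 × 0.329 × 0.671 / 389) = 0.03369
- Alternative SE = √(0.4371 / 389) = 0.03352
- Power = Φ[(0.094 − 1.960 × 0.03369) / 0.03352] = Φ(0.834) = 79.8%

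**Effect of adjustment.** Let R² be the share of outcome variance explained by baseline values. The documents give no such figure, so R² is an assumption. The variance of the adjusted risk difference is approximately (1 − R²) times the crude variance, so both SEs are multiplied by √(1 − R²). At R² = 0.10 the factor is 0.949 and power = Φ[(0.094 − 0.06264) / 0.03180] = Φ(0.986) = 83.8%.

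| Assumed R² | 95% CI half-width of ARD (points) | Power at 389 per group | Gain (points) | Total N for the precision of 778 crude |
|---|---|---|---|---|
| 0 | 6.6 | 79.8% | 0 | 778 |
| 0.02 | 6.5 | 80.6% | 0.8 | 764 |
| 0.05 | 6.4 | 81.8% | 2.0 | 740 |
| 0.10 | 6.2 | 83.8% | 4.0 | 702 |
| 0.15 | 6.1 | 85.8% | 6.0 | 662 |

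**Simulation check.** One normal covariate, 389 per group, 3,000 runs per setting, logistic model standardized to the risk difference. The Monte Carlo SE of power is about 0.7 points.

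| R² | Power, crude | Power, adjusted | Variance ratio |
|---|---|---|---|
| 0 | 80.7% | 80.6% | 1.00 |
| 0.02 | 79.6% | 80.3% | 0.985 |
| 0.053 | 80.9% | 82.2% | 0.968 |
| 0.107 | 80.8% | 85.0% | 0.902 |
| 0.167 | 79.4% | 85.8% | 0.833 |

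With no treatment effect, rejection rates were 5.3% crude and 5.2% adjusted at R² 0.053, and 5.1% and 4.8% at R² 0.167. A separate simulation indexed by AUC (4,000 runs) agrees. At AUC 0.61 the variance ratio is 0.97 and power goes from 79.8% to 81.7%. At AUC 0.70 the ratio is 0.88 and power goes from 79.3% to 84.3%.

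**Per-protocol exclusions (assumed rates).** With 5% excluded, crude power is 77.7%, and 81.9% after adjustment at R² 0.10. With 10% excluded, the figures are 75.5% and 79.8%.

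**Can the model carry the covariates?** Expected events: 389 × (0.376 + 0.282) ≈ 256. Arm, 12 center indicators, risk stratum, age, APACHE II and one oxygenation value make 17 terms, or about 15 events per term.

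**Limits of the check.** Neither simulation includes center or risk stratum, several covariates together, missing values or per-protocol exclusions. They compare an adjusted with a fully crude analysis.

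**The case against.** The strongest reply is that nothing in the plan is wrong. The crude test holds its error rate, which already allows for chance imbalance, and the trial was sized for exactly that test. This stands: a reader might infer that the chi-square is invalid or the trial undersized, and the recalculation contradicts both.

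Second, a reader might infer a definite loss of precision. The documents do not support that, because they link no baseline value to major complications. At R² 0.02 the gain is under 1 point. Oxygen was regulated to keep saturation over 90%, so saturation may vary little, and it bears more directly on desaturation than on upper airway obstruction or vomiting.

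Third, a reader might take the tabulated gains as additional to adjustment for the strata. That was not computed, and age and APACHE II already feed the risk flag.

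Fourth, the contents of the monitoring sheet are not listed, so saturation being on it is an inference. The oxygen setting is given as a flow rate or FiO₂, which are not one scale.

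Fifth, the order of events is unclear. The main-text Procedure and Interventions section and the Supplementary spontaneous breathing trial section put randomization immediately after the trial, while the Supplementary Procedure puts the recording before randomization. Age and the previous day's APACHE II are unaffected.

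Sixth, the validity of adjustment rests on the randomized comparison, whereas the primary set is per-protocol.

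These points narrow the claim and shape the remedy. They do not remove it: usable baseline values exist, the analysis ignores them, and including them cost nothing material in the simulation even when they predicted nothing.

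**Conclusion.** The point holds as an efficiency improvement, not as a validity error. The planned primary comparison is unadjusted and may give up precision that the trial's own baseline data could recover for the same RR and ARD.

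The gain is negligible if the baseline values are weak predictors and becomes material from roughly R² 0.10, where it would offset about 10% per-protocol exclusions. These figures rest on an assumed R², the (1 − R²) variance approximation, complete data and analysis as randomized.

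**What to change.** In Statistical analysis, make the primary estimate a prespecified covariate-adjusted marginal RR and ARD, with the chi-square result kept as supportive.

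- **Model:** logistic regression standardized over all analysed patients. In SPSS, an alternative is Poisson regression with robust standard errors for RR and a linear model with robust standard errors for ARD.
- **Terms:** arm, center, high/low risk, continuous age, continuous APACHE II, and the preextubation oxygenation value if it is on the sheet. Use the oxygen setting at the end of the breathing trial only if it is put on one common scale. State in advance how centers with few events are pooled.
- **Data checks:** confirm that the monitoring values were recorded before randomization and reconcile the sections that differ on the order. Confirm that APACHE II is held as a score for every patient, since one other criterion is enough to classify a patient as high risk.
- **Missing baseline values:** one simple rule that ignores arm, such as the overall median.
- **Populations:** apply the same model to the intention-to-treat analysis.

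The cost is a paragraph of text, a few lines of code and the discipline of fixing covariates and model in advance. No new patients or visits are needed. The documents are in the past tense, with admissions ending in March 2020. If the data are already unblinded, leave the primary analysis as planned and report the adjusted estimate as a labelled sensitivity analysis.

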### References

### Supplementary Material

Spontaneous breathing trial

Patients who met the eligibility criteria and successfully completed the spontaneous breathing trial (SBT) were immediately randomized. It was conducted with a T-tube, by applying continuous positive airway pressure (continuous positive pressure in the airway) at 5 cm H2O, or by applying pressure support (PS) from 5 to 8 cm H2O for a period ranging from 30 to 120 minutes. The oxygen flow rate or FiO2 was regulated to keep an oxygen saturation over 90%. After extubation, supplementary oxygen was administered with the same FiO2 used at the end of the successful SBT. All variables were collected and recorded in specific forms.

### Interventions

Both procedures were performed by two operators. In the traditional orotracheal traditional extubation (OTE), a closed suction system catheter was placed into the endotracheal tube (ETT) by the first operator, and endotracheal suctioning (ES) was initiated. The cuff was immediately deflated by the second operator, and the ETT was removed with continuous ES during the entire procedure. In the positive pressure OTE, the first operator set the ventilator parameters to PS ventilation mode, with an inspiratory pressure of 15 cm H2O and a positive end expiratory pressure (PEEP) of 10 cm H2O. Then, the cuff was deflated by the second operator, and the suction catheter was introduced through the mouth to suction secretions drawn to the oropharynx while the ETT was removed by the first operator without applying ES. Before the study, the participating centers were trained in both OTE procedures by means of videos.

### Procedure

Patients were included in the study once they had successfully completed the SBT and met the OTE criteria. The blinded evaluator followed a preextubation checklist. It entailed discontinuing enteral nutrition, adjusting the head of the bed to 45°, suctioning oropharyngeal and tracheobronchial

secretions, and recording preextubation monitoring on the pertaining sheet. Regardless of the procedure, the alarms were silenced, and the ventilator parameters were set at PS 15/10 cmH2O by one operator, so that the blinded evaluator could not hear the maneuver or read the ventilator parameters. The blinded evaluator left and was replaced by the operators, who knew about the technique assigned. They initiated the randomization through <http://extubar.ajrpt.com> and were in charge of the OTE and postextubation oxygen delivery. Regardless of the OTE technique, the patients received supplemental oxygen through a nasal cannula placed before ETT removal to keep the oxygen flow used in the SBT.

Once the OTE was completed, the blinded evaluator assessed the outcome measures recorded within 60 min after extubation. Daily monitoring of outcome measures within 72 h after extubation was carried out.

The decision to perform OTE and to use NIMV or HFNC to prevent OTE failure, follow-up, and treatment was taken by the blinded evaluator, or the respiratory therapist on duty, who was blinded to randomization assignment. If preventive NIMV or HFNC had previously been decided, it was implemented 15 min after OTE so as not to affect monitoring of outcome measures.

## Randomization

The randomization sequence was generated before the study by using the web site (<https://www.sealedenvelope.com/>) in blocks of 6 and stratified by participating center and by the risk of extubation failure (high or low). High risk of extubation failure was defined as the presence of at least one of the following criteria: age  $\geq 66$  years, moderate or severe chronic obstructive pulmonary disease (COPD),  $\geq 2$  comorbidities (COPD, peripheral artery disease, immune deficiency, liver disease, hypertension, diabetes, neurological disease, heart failure, chronic renal failure), body mass index (BMI)  $\geq 31$ , congestive heart failure as main reason from IMV, difficult intubation, IMV  $\geq 8$  days, a requirement of suctioning respiratory secretions ( $\geq 3$  suctions within 4 h before the OTE), difficult or prolonged

weaning and/or APACHE II (*Acute Physiology and Chronic Health disease Classification System II*) a day before the OTE  $\geq 13$ . Randomization assignment was blinded to researchers in charge of recruiting patients through an online platform (<http://extubar.ajrpt.com>).

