## Methods

### Design

A multicenter randomized clinical trial was conducted in 13 centers from Argentina. Patients admitted to the intensive care units (ICU) between April 1, 2019, and March 26, 2020, were included in the analysis. Our study was evaluated and approved by the Research Ethics Committee (#12-2018-05, approved on February 28, 2019) and registered on ClinicalTrials.gov (NCT03918811, April 18, 2019). The results were reported according to the CONSORT Statement for reporting randomized clinical trials [13].

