### Procedure and Interventions

Patients who met the eligibility criteria and successfully completed the SBT were immediately randomized. Once OTE was performed by two operators, assessment of outcome measures within 60

min after extubation was done by a third operator (blinded). Daily monitoring of outcome measures within 72 h after extubation was performed by this same operator. If preventive NIMV or high flow nasal cannula (HFNC) had been decided, they were initiated 15 min after OTE in order not to influence monitoring of outcome measures. Extubation maneuvers were performed in accordance with the procedure reported in the literature [11]. The traditional OTE technique consisted of deflating the cuff and removing the ETT by applying continuous endotracheal suctioning during the entire procedure. In positive pressure extubation, ventilator parameters were set at 15/10 cmH2O, in PC-CSV mode. The cuff was deflated, and a suction catheter was introduced through the mouth to suction secretions from the oropharyngeal cavity [11,18,19] while the ETT was removed without endotracheal suctioning (see supplementary material).

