#### Randomization

Randomization was performed in blocks and stratified by participating center and by the risk of extubation failure (high or low), as reported in prior studies [16,26]. Randomization assignment was blinded to the operators in charge of the procedures through an online platform (see supplementary material).

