#### Blinding

Due to the nature of the intervention, blinding of patients and operators performing OTE was not possible. The evaluator who recorded measures of interest after extubation was blinded to the assigned extubation technique. The database was monitored by third parties with no direct participation in the study and no interest in its outcomes. The data were analyzed pursuant to the statistical analysis plan devised before the study, and the person in charge of data statistical analysis was blinded to the technique used.

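### Fixed blocks of 6 in each centre-by-risk list leave up to a quarter of allocations deducible by site staff who know the block size and list history, and the main text wrongly describes the operators as blinded

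*Combined protocol and SAP*

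**What the plan says.** Supplementary Material, Randomization, gives one block size: the sequence was generated "in blocks of 6 and stratified by participating center and by the risk of extubation failure (high or low"). Methods, Randomization, repeats the stratification without the size. Methods, Design, gives the number of centres: "A multicenter randomized clinical trial was conducted in 13 centers from Argentina". No section says that block size varied or that it was withheld from sites.

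The sections describe who knew the allocation differently:

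- Methods, Randomization: "Randomization assignment was blinded to the operators in charge of the procedures through an online platform".
- Methods, Blinding: "blinding of patients and operators performing OTE was not possible".
- Supplementary Material, Procedure: "The blinded evaluator left and was replaced by the operators, who knew about the technique assigned". The same operators start the randomization on the platform.
- Supplementary Material, Randomization: the people blinded are the researchers who recruit.

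The supplement's Procedure section assigns the decision to extubate to the blinded evaluator or a blinded therapist on duty. Methods, Procedure and Interventions, says that outcome assessment "after extubation was done by a third operator (blinded").

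**The concern.** Blocking balances the arms by making later allocations in a block depend on earlier ones. When every block has the same known length, a person who has followed the list can sometimes name the next arm with certainty. The operators learn each allocation as it is made, so the information exists at the site.

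Two things could be at stake. The first is concealment: foreknowledge could affect which patient is randomized, or when. The second is assessment of the primary outcome, a composite of clinical evidence of desaturation, upper airway obstruction or vomiting. Operators and patients are unblinded, so concealment and the evaluator's blinding carry most of the protection against bias. The safeguards described (the evaluator leaves, alarms are silenced, ventilator settings are the same in both arms) stop the evaluator from seeing or hearing the current manoeuvre. They do not address inference from past assignments.

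In addition, a statement that the operators were blinded credits the design with a property it does not have.

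**Working it through.** **Inputs.** Block size 6 (supplement, Randomization). 13 centres (Methods, Design). Two risk strata. From Methods, Sample size: "778 patients (389 per group) were required to have an 80% chance of detecting, as significant at the 5% level", for 37.6% against 28.2%. A 1:1 ratio is inferred from the equal groups.

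**The plan's own figure.** With unpooled variance, n per group = (1.960 + 0.842)² × (0.376 × 0.624 + 0.282 × 0.718) / 0.094² = 388.3. This rounds up to 389 per group, or 778, so the stated size is reproduced.

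**Lists.** 13 × 2 = 26. The mean list is 778 / 26 = 29.9 patients, about five blocks.

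**Certain allocations in a block of 6.** There are C(6,3) = 20 equally likely blocks. An allocation is certain once one arm has its three places filled.

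| Position | Chance of being certain |
|---|---|
| 1 to 3 | 0 |
| 4 | 2/20 = 0.10 |
| 5 | 8/20 = 0.40 |
| 6 | 1.00 |

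The sum is 1.5 of 6 = 25%. The general formula 1/(b/2 + 1) with b = 6 gives the same. Applied to the trial, 0.25 × 778 = 194.5.

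**Best guess.** Always guessing the arm that is behind in the block succeeds in [3 + (64/20 − 1)/2] / 6 = 4.1/6 = 68.3% of allocations.

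**What lowers the 25%.**

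- Unfinished blocks: a list of 10 gives (1.5 + 0.1)/10 = 16%, and a list of 5 gives 0.5/5 = 10%. Simulating 778 patients over uneven centres (assumed sizes, high-risk share 50% to 90%) gives about 23%.
- Partly known history: suppose the position is known but each earlier assignment is seen only with probability q (assumed). Certainty needs all three of one arm to have been seen, so the share is 0.25 × q³. This is 10.5% for q = 0.75, 3.1% for q = 0.50 and 0.4% for q = 0.25.
- No history seen: 0%.

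**Varying block sizes.** This was simulated on lists of 30, for an observer who sees the full history and knows the set of sizes but not the order.

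| Block sizes | Certain | Best guess correct |
|---|---|---|
| 6 | 25.0% | 68.3% |
| 4, 6 | 5.9% | 68.8% |
| 4, 6, 8 | 2.3–2.4% | 67.4–67.5% |

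With sizes 4, 6 and 8, about 18 or 19 of 778 allocations would be certain. Almost all of the gain is in certainty. Ordinary guessing hardly changes.

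**Power without the determined allocations.** 0.75 × 389 = 292 per arm. The standard error is √[(0.2346 + 0.2025)/292] = 0.0387, and 0.094/0.0387 − 1.96 = 0.47, so power is about 68%.

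**The case against.** The strongest reply is that the 25% needs one person who knows the block size, the position and every earlier assignment in the list, and that no section says such a person existed. The people who could use the knowledge (recruiters, those deciding on extubation, and the evaluator) are all described as blinded. Randomization follows a successful breathing trial immediately, which narrows the room to choose the timing. Tracking is also slow. The inclusion window is 360 days, so with even accrual (assumed) a list receives one patient every 360/29.9 = 12 days and a block takes about 10 weeks, separately for high and low risk. All of this stands, and it makes the 25% a ceiling.

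Three stronger readings are tempting but unsupported.

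- A reader might infer that a quarter of allocations were in fact known in advance. The documents do not say that sites knew the block size or that the platform displayed earlier assignments.
- A reader might take the phrase about a third operator to mean that one pool of staff rotated through all the roles. It only counts the people present at one extubation, and says nothing about rotation between patients.
- A reader might attach an inflated error rate. A 10-point bias in every determined allocation would shift the comparison by 0.25 × 10 = 2.5 points and raise the two-sided error from 5% to about 11% (37.6% against 35.1%, 389 per arm). The 10 points are an assumption, and nothing in the documents indicates such a bias.

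It can also be said that the main-text sentence on operators was meant to say that allocation was hidden until they opened it. That may be so, but the sentence does not say it, and two other sections contradict it as written.

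**Conclusion.** The point holds in a limited form. One block size of 6 in each of 26 derived lists, opened by unblinded operators, makes up to 25% of allocations (about 194 of 778) deducible by staff who know the block size and the full list history. About 23% is more realistic with unfinished blocks, and the share falls steeply when history is only partly known. It is a possible risk to concealment. It becomes a risk to the evaluator's blinding only if knowledge passes between staff or roles change between patients, and the documents are silent on both. No breach is shown and no bias in the result can be inferred.

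The contradiction over the operators' blinding depends on none of these assumptions and needs correcting in any case.

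**What to change.** 1. In Supplementary Material, Randomization, generate each centre-by-risk list with randomly varying block sizes, for example 4, 6 and 8, not disclosed to sites. This is a setting at list generation and costs no patients or staff time. The downside is slightly more possible imbalance at the end of a stratum: at most 4 in a list whose last block is of size 8, against 3 with blocks of 6.
2. In Methods, Randomization, state that allocation was concealed from recruiting and evaluating staff and that the operators were not blinded, in line with Methods, Blinding and the supplement's Procedure and Randomization sections. State also whether sites knew the block size and whether operator, recruiter and evaluator roles stayed separate across patients. This costs a few sentences.
3. Methods, Design, describes inclusion as complete. If the lists have already been used, step 1 applies only to future lists. In that case report a supportive sensitivity analysis of the primary outcome that leaves out fully determined allocations. Identify them from the full randomized sequence, not from the per-protocol set, because excluded patients still occupy places in a block. Compare the estimate with the main one and do not rely on its p-value, since power is about 68% at about 292 per arm. This analysis does not remove allocations that were merely guessable.
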